5.5.4 Instructions for prescribing and taking study treatment

Subcutaneous (s.c.) injections are to be given for each investigational product administration. For purposes of study treatment dosing, “q.m.” refers to an every 4 weeks injection regimen. The study drug administration date should be in 4 week increments (+/- 5 days) from the first dose of study drug. Any dose administrations that may occur greater than +/- 5 days from the 4 week time point (e.g., patient unavailability) should be discussed with the Sponsor prior to dosing. The anatomical sites for administration of investigational product are the upper arm, upper thigh, or abdomen; the location of the injection sites should be documented in the source document.

Double-Blind Treatment Epoch:

Two injections of AMG 334 70 mg (equaling 140 mg total dose) or placebo will be administered by qualified study staff at each dosing visit during the 12-week double-blind treatment epoch (i.e., at Day 1 and Weeks 4 and 8).

Open-label Treatment Epoch and PTA-Open-Label Treatment Epoch:

Two injections of open-label AMG 334 70 mg (equaling 140 mg total dose) will be administered by qualified study staff at each dosing visit during the 156-week open-label treatment epoch (ie, at Weeks 12, 16, 20, 24, etc.) and during the PTA-Open-Label Treatment Epoch (ie, at Weeks 168, 172, 176, 180 etc.). If and when 140 mg/mL pre-filled syringes become available during the Open-Label Treatment Epoch, the 140 mg dose may be administered by a single 140 mg/mL s.c. injection.

The investigational product dose is fixed and will not be adjusted for individual patients during the study. There are no temporal restrictions for study drug administration (e.g., proximity to meals, sleep or activity).

All kits of study treatment assigned will be recorded in the IRT. Novartis monitors will reconcile treatment assigned vs treatment administered and ensure that the information is congruent during their monitoring visits.

During the **COVID-19 pandemic** that limits or prevents on-site study visits, delivery of study drug directly to a patient’s home is generally permitted in the event the Investigator has decided that an on-site visit by the patient is no longer appropriate or possible, and that it is in the interest of the patient’s health to administer (e.g., self-injection or study staff administration at patients’

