Study Day 1 is defined as the first investigational product (IP) dose date. For subjects who are randomized but not dosed after randomization, the Study Day 1 is defined as the date of randomization.

Study Day is defined as the number of days from Study Day 1.

Before Study Day 1:

$$\text{Study Day} = (\text{Date of Interest} - \text{Date of Study Day 1})$$

On or after Study Day 1:

$$\text{Study Day} = (\text{Date of Interest} - \text{Date of Study Day 1}) + 1$$

Therefore the day prior to Study Day 1 is -1.

Last date of patient contact

The date of last patient contact will be selected as the minimum of the following non-missing dates:

1. 'Date of Discontinuation/study phase completion', either from the study completion page or
2. The treatment epoch completion page if calculated specifically for a study epoch.

Duration of Migraine

The duration of migraine in years (migraine with aura or migraine without aura, whichever is earlier) is calculated by the following formula: current age (in years) - age at migraine onset (in years).

Current age is calculated by the following formula, the date of informed consent – birth date (at least the year).

If the current age calculated as detailed above or the age at migraine onset is missing then duration of migraine will be missing.

Duration of exposure to AMG 334

For all calculations of exposure, dose date refers to receiving dose > 0, but can include partial doses.

Duration of DB IP Exposure

If subject enters into the open-label treatment phase,

Duration = Minimum (Last DB Dose Date + 27, First OLTP Dose Date, EoS Date-1) – First DB Dose Date+1

Otherwise,

Minimum (Last DB Dose Date + 27, EoS Date) – First DB Dose Date+1

Duration of OL IP Exposure

Minimum (Last OLTE Dose Date + 27, EoS Date) – First OLTE Dose Date+1

Subject Incidence

The subject incidence for a given event in a given period is defined as the number of subjects with at least one reported occurrence of the event divided by the number of subjects who entered that period. For subjects with multiple occurrences of the same event, the event will only be counted once per subject.

Exposure-Adjusted Subject Incidence Rate

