Listings will include all assessments, sorted by scheduled visit and time of assessment, flagging unscheduled visits. The listings will include analysis windows and corresponding flags to indicate the assessment's inclusion in analysis.

Further details regarding analysis windows for specific domains are included in Tables below.

Monthly Interval for Efficacy Endpoints

Monthly efficacy measurements will be calculated based on the subject's monthly investigational product(IP) dosing schedule defined below using eDiary data collected from beginning of the baseline phase (week -4 visit) up to open label treatment period.

Table 2 Study Intervals for Efficacy Endpoints

Study Phase	Assessment Timepoint	Interval Based on Dose Dates	
		Start date	End date
Baseline Epoch	Baseline	From eDiary device assignment date (or Week -4 visit)	Day prior to study day 1
Double-Blind Treatment Epoch	Week 4	Study Day 1	
 • Week 4 dose date-1 • Study day 28 if Week 4 dose is not received (either missed or IP discontinued prior to Week 4) 
Note: if day 1 dose is the last IP dose subject received, the rest of monthly rates during DBTE will be calculated based on consecutive 28-day interval beginning on study day 29 (ie, 29-56 for week 8, 57-84 for week 12)

	Week 8	
 • Week 4 dose date 
Study day 29 if Week 4 dose is not received (either missed or IP discontinued prior to Week 4)
	
 • Week 8 dose date-1 
Study day 56 if Week 8 dose is not received (either missed or IP discontinued prior to Week 8)

	Week 12	
 • Week 8 dose date 
Study day 57 if Week 8 dose is not received (either missed or IP discontinued prior to Week 8)
	
 • Week 12 IP dose date-1 • If Week 12 dose is not received (either missed or IP discontinued prior to Week 12) 
 ○ MIN (Study day 84, EOS) if Week 8 dose is not received ○ MIN (Week 8 dose date + 27, EOS) if week 8 dose is

			received
--	--	--	----------

Study Visit

Since the actual visit for a subject may not exactly coincide with their targeted visit date, the actual visit date is mapped to a study visit.

The next study day window will be utilized to define study visit for lab, vital signs, C-SSRS and some PROs collected during office visits [REDACTED] before dose is administered [REDACTED]

Table 3 Study Visit Windows

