Study visit	Target Day	Study Day for vital signs, C-SSRS (for lab [REDACTED] include only Day1, Week 12, 24, 64)	Study Day [REDACTED]
Baseline	Please refer to Section 2.1.1		
Day 1	1	1	1
Week 4	29	16-43	16-43
Week 8	57	44-71	44-71
Week 12	85	1.72 to (week 12 OLTE dose date) for subjects who receive OLTE dose at week 12 2.72-99 for subjects who did not receive OLTE dose at week 12	1.72 to (week 12 OLTE dose date) for subjects who receive OLTE dose at week 12 2.72-99 for subjects who did not receive OLTE dose at week 12

For safety analyses which are summarized by study phase, analysis windows will be set up based on study phase:

Table 4 Study Phases for Safety analysis

Study Phase	Start Time Point	End Time Point
Double-blind Treatment Epoch	Study Day 1 (after the 1st DB IP Dose)	
 • First OLTE Dose Date - 1 for subjects receive OLTE IP dose; • MIN(EoS Date, last IP dose date + 84 days) for subjects did not receive any OLTE IP dose

Note: all anti-AMG 334 antibody data during all epochs will be included in immunogenicity analysis.

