2.7.3 Columbia-Suicide Severity Rating Scale (C-SSRS)

No statistical testing will be performed on C-SSRS. The number and percentage of subjects reporting any suicidal ideation and any suicidal behavior will be summarized descriptively by treatment group for DBTE. Shift table of C-SSRS maximum severity of suicidal ideation/behavior compared to baseline will be provided by treatment group for DBTE.

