2.7.4 Electrocardiogram (ECG)

The ECG measurements from this clinical study were performed as per standard of care for routine safety monitoring, rather than for purposes of assessment of potential QTc effect. Subject incidence of abnormal ECG diagnosis will be summarized by treatment group separately for the DBTE. However, since these evaluations may not necessarily be performed under the rigorous conditions expected to lead to meaningful evaluation of QTc data, these data are not expected to be useful for meta-analysis with data from other trials.

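### SAP Tables 3 and 4 place the Week 12 dosing day on opposite sides of the double-blind boundary, so the phase-level ECG and C-SSRS outputs would omit Visit 199 if Table 4 is applied literally

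*SAP*

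**What the plan says.** SAP section 2.1.1 sets two kinds of safety window.

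- **By visit (Table 3).** It is introduced with "The next study day window will be utilized to define study visit for lab, vital signs, C-SSRS and some PROs collected during office visits". For patients dosed open-label at Week 12, the Week 12 window runs from Day 72 to the open-label dose date, with that date included.
- **By phase (Table 4).** It is introduced with "For safety analyses which are summarized by study phase, analysis windows will be set up based on study phase". The double-blind phase starts on Study Day 1 after the first dose. For patients who go on to open-label treatment it ends at "First OLTE Dose Date - 1 for subjects receive OLTE IP dose". A note under the table keeps antibody data from all epochs.

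Protocol section 5.5.4 schedules open-label dosing "ie, at Weeks 12, 16, 20, 24, etc". Protocol Table 6-2 opens with Visit 199/Week 12, which carries study drug, ECG, C-SSRS, chemistry/haematology, vital signs and weight. Its first footnote asks for all procedures of a visit to be completed on the same day.

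Two outputs are described for the epoch as a whole, with no by-visit version:

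- SAP 2.7.4: "Subject incidence of abnormal ECG diagnosis will be summarized by treatment group separately for the DBTE".
- SAP 2.7.3: counts of any suicidal ideation and any suicidal behaviour for the epoch, and "Shift table of C-SSRS maximum severity of suicidal ideation/behavior compared to baseline will be provided by treatment group for DBTE".

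**The concern.** The Week 12 ECG and C-SSRS are scheduled for the date of the first open-label dose. Table 4 closes the phase one calendar day earlier, and no visible rule carries that day's pre-dose assessments back into it. Table 4 splits Day 1 by the dose itself, but cuts the other end by date.

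What is at stake is the last placebo-controlled ECG and C-SSRS, taken after all three double-blind doses. A maximum-severity table is sensitive to a dropped visit. SAP 2.1.2 includes a Since Last Visit version of the C-SSRS, so the Week 12 form asks about the time since Week 8, which is double-blind time. Two programmers following the SAP could produce different ECG and C-SSRS tables.

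**Working it through.** The SAP states no figure to reproduce here. The check compares date windows and counts scheduled assessments.

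**1. Is Visit 199 inside each window?** Let D be the study day of the first open-label dose, which is the Visit 199 day on schedule. The target is Day 85 (Table 3), and Protocol 5.5.4 allows ±5 days, so D runs from 80 to 90.

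- Table 3, Week 12: 72 ≤ D ≤ D is true for every D from 80 to 90.
- Table 4, double-blind phase: 1 ≤ D ≤ D − 1 is false for every D.

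On schedule, Table 3 covers Days 72–85 and Table 4 ends on Day 84.

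**2. How many patients?** The protocol's Amendment 3 rationale gives 246 randomised, 242 completing the double-blind epoch and 240 continuing. 240/246 = 97.6% of randomised patients, and 240/242 = 99.2% of completers.

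**3. What does a literal Table 4 cut leave?** Scheduled post-baseline double-blind assessments are counted from Protocol Table 6-1 and SAP Table 14.

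| Assessment | Scheduled | Left under Table 4 | How the SAP summarises it | Affected? |
|---|---|---|---|---|
| ECG | Weeks 4, 12 | 1 of 2 | Incidence for the epoch (2.7.4); not named in visible Table 3 text | Yes |
| C-SSRS | Weeks 4, 8, 12 | 2 of 3 | Counts and shift for the epoch (2.7.3) | Yes |
| Vital signs | Weeks 4, 8, 12 | 2 of 3 | Over time and at each time-point (2.7.5) | No, Table 3 applies |
| Weight | Week 12 | 0 of 1 | Over time (2.7.5) | No, Table 3 applies |
| Laboratory | Week 12 | 0 of 1 | Over time (2.7.2) | No, Table 3 applies |
| Liver categories | Week 12 | 0 of 1 | Labelled neither by visit nor by phase (2.7.2) | Only if run by phase |
| Antibodies | Week 12 | – | All epochs kept (note to Table 4) | No |

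**4. Does double-blind exposure conflict with Table 4?** For patients entering open-label treatment, the end point in SAP 2.1.1 is "Minimum (Last DB Dose Date + 27, First OLTP Dose Date, EoS Date-1"). On schedule the last double-blind dose is Day 57 and the first open-label dose is Day 85. Then 57 + 27 = 84, which is below 85 and equals 85 − 1. The formula therefore agrees with Table 4. The open-label dose date becomes the minimum only when it falls 27 days or fewer after the last double-blind dose.

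**The case against.** **The day-before boundary is deliberate.** On schedule the exposure formula gives the same Day 84, and Table 2 ends the Week 12 efficacy interval the day before the Week 12 dose. Only Table 3 differs. A day-before cut is also reasonable for adverse events, which have recorded start dates. This stands, and it is why the boundary should remain for event onset. It does not justify excluding an ECG or C-SSRS scheduled as the final double-blind assessment.

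**Naming the epoch need not invoke Table 4.** SAP 2.7.5 describes vital signs over time separately for the same epoch, which is a by-visit analysis. Protocol 5.6.1 defines completion of the epoch as completing Visit 199, and SAP Table 14 lists that visit under double-blind treatment. C-SSRS is named in Table 3. This makes it likely that the authors meant to include Visit 199. The phase windows are nevertheless defined by date, and neither the ECG nor the C-SSRS section gives a by-visit output that Table 3 would govern.

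**Redaction.** The text before Table 3 has a visible fragment about the time before dosing, between blacked-out parts, and the table header is also partly hidden. A pre-dose convention or a mention of ECG could lie there. This limits certainty.

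**Stronger readings that the documents do not support.**

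- A reader might infer that the whole controlled safety comparison loses Week 12, including the only scheduled post-baseline laboratory sample. The by-visit summaries follow Table 3 and keep it.
- A reader might infer that ideation reported by placebo patients at Visit 199 would be attributed to open-label AMG 334. Table 4 shows only the double-blind phase, and SAP section 1 leaves the open-label analysis to a separate plan that is not available here.

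**Conclusion.** The point holds for a limited set of outputs. Tables 3 and 4 assign the Week 12 dosing day differently. If Table 4 is applied literally, the abnormal-ECG incidence loses 1 of 2 scheduled post-baseline double-blind ECGs, and the C-SSRS counts and maximum-severity shift lose 1 of 3 assessments. The liver-category table remains an open question, because the SAP does not say which window it uses.

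Up to 240 of 246 patients are affected. That number assumes their first open-label dose was given on the Visit 199 day as scheduled; actual dates are not given. The conclusion also assumes that the redacted text holds no rule that settles the matter. No primary or secondary efficacy analysis is touched. Because the conflict lies in the stated windows and is cheap to remove, it should be corrected.

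**What to change.** Keep the Table 4 cut-off, the day before the first open-label dose, for adverse-event onset. Add one rule: scheduled Visit 199 ECG, C-SSRS, laboratory and vital-sign assessments dated on the first open-label dose date, and made before that dose, count as double-blind, matching Table 3. State in SAP 2.7.2, 2.7.3 and 2.7.4 that the liver-category, C-SSRS and ECG tables use this rule.

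The cost is a short SAP clarification and a programming flag. No new data are needed. The downside is that a few same-day measurements actually taken after the dose could be counted as double-blind.

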5.6 Study completion and discontinuation

5.6.1 Study completion and post-study treatment

A patient will be considered to have completed the Double-Blind Treatment Epoch when the patient has completed Visit 199 in the protocol. A patient will be considered to have completed the Open-Label Treatment Epoch when the patient has completed Visit 299 in the protocol. A patient will be considered to have completed the PTA-Open-Label Treatment Epoch when the patient has completed Visit 499 in the protocol.

Patients can stay in the Open-Label Treatment Epoch for 156 weeks (3 years), or until the study is early terminated by the sponsor. Patients may stay in the PTA-Open-Label Treatment Epoch as specified in [Section 3.1](#).

The study will be considered complete (End of Trial) when the last patient completes their last visit (i.e., LPLV) in the study.

The patient's completion status will be recorded on the appropriate Study Phase Completion eCRF pages.

For all patients not continuing on AMG 334, either in the Open-Label Treatment Epoch or commercially, outside the study (if locally available), a safety follow-up visit (visit 301) should be conducted 16 weeks after the last AMG 334A dose administration. The information to be collected at this follow up visit is outlined in [Table 6-1](#), and [Table 6-4](#).

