Week	12	16	20	24	28	32	36	40	44	48	52	56	60	64
C-SSRS	X	X	X	X	X	X	X	X	X	X	X	X	X	X
Concomitant Medications	X	X	X	X	X	X	X	X	X	X	X	X	X	X
Adverse Events ¹⁰	X	X	X	X	X	X	X	X	X	X	X	X	X	X
Serious Adverse Events ¹⁰	X	X	X	X	X	X	X	X	X	X	X	X	X	X
Study Drug Administration ¹¹	X	X	X	X	X	X	X	X	X	X	X	X	X	X
Contact IRT ¹²	X	X	X	X	X	X	X	X	X	X	X	X	X	X

- 1 – All study visit target dates are to be calculated from the Day 1 visit date, and all study procedures for a given visit should be completed in the same day.
 2 – The Follow-Up Visit is required for all patients who either discontinue study drug early or complete the study and do not continue commercial drug (if locally available) in either the Double-Blind or Open-Label Treatment Epochs.
 3 – Entry into the Open-Label Treatment Epoch can occur only if the patient successfully completes all requirements for the Double-Blind Treatment Epoch.
 4 – Includes blood pressure, pulse and temperature.
 5 – eDiaries will be used for the first 12 weeks of the Open-Label Treatment Epoch and again at periodic intervals as identified in the assessment schedule.
 6 - Daily collection during the respective 4 week periods
 7 - HRQ collection after migraines during the respective 4 week periods

10 - SAEs will be collected after signing of the informed consent through the end of the Follow-Up Epoch end of study (16 weeks after the last dose of study drug). Non-serious AEs will be collected after randomization (Visit 101) through the end of the Follow-Up Epoch (16 weeks after the last dose of study drug).

11 – Two pre-filled syringes will be administered by study staff, during the applicable study visits, q.m., s.c..

12 - Sites will access the Interactive Response Technology (IRT) System to enter the patient into the open-label treatment phase and to register study early termination.

X = Assessment to be recorded in the source documents and the clinical data base; S = Assessment to be recorded as source documentation only.

Table 6-5 Assessment Schedule – PTA-Open-Label Treatment

Epoch		PTA Open-Label Treatment						499 ² / End PTA
		Initial 3 month cycle			Repeat 3-Month cycle until end of PTA			
Visit	299	401	402	403	404	405	406	
Weeks	168	172	176	180	184	188	192	
Study drug administration	X	X	X	X	X	X	X	
Contact IRT	X	X	X	X	X	X	X	
Adverse Events/ Serious Adverse Events	X	X	X	X	X	X	X	X
Concomitant medications / therapies	X	X	X	X	X	X	X	X
Clinical Global Impression - Severity	X							

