1.1 Study design

[figure not shown]
This study uses a single-cohort, 2-treatment arm, parallel-group randomized, double-blind, placebo-controlled design in adult patients with episodic migraine who have previously failed 2 to 4 prophylactic migraine treatments. The following epochs are included in the study design, with study visits at 4 week intervals after completion of screening:

- **Screening Epoch (0-2 weeks)** – Required for all patients to assess initial eligibility.
- **Baseline Epoch (4 weeks)** – All patients successfully completing the Screening Epoch are invited to participate. Eligibility for randomization will be assessed based on migraine frequency and diary compliance during this epoch.
- **Double-Blind Treatment Epoch (12 weeks)** – All patients successfully completing the Baseline Epoch are invited to participate. Eligible patients will be randomized to one of two treatment arms. At the end of this epoch (Week 12), the final assessment to address the efficacy-related objectives will occur.
- **Follow-Up Epoch (12 weeks)** – Unless patients continue onto commercial AMG 334 after completing the Double-Blind and/or Open-Label Epochs (contingent upon marketing authorization and commercial availability in the participating country), a Follow-Up Visit 16 weeks after the last dose of AMG 334 will be required as part of routine safety monitoring.

Randomization will be stratified by migraine frequency reported during the Baseline Epoch: 4-7 vs 8-14 migraines per month based on eDiary calculations.

The primary analysis will be triggered when the last patient completes the Double-Blind Treatment Epoch (DBTE). The database will be locked once when the last patient has completed the DBTE. Data of the DBTE will be summarized in a study report. A separate analysis will occur at the conclusion of the Open-Label Treatment Epoch.

Figure 1 Study design

Patients will receive either AMG 334 140 mg qm sc or matching placebo for 12 weeks in the Double-Blind Treatment Epoch, followed by a 3-year Open-Label Treatment Epoch of AMG 334 140 mg qm sc.

[figure not shown]
The primary objective is to evaluate the effect of 140 mg AMG 334 compared to placebo on the proportion of patients with at least 50% reduction from baseline in monthly migraine days in the last month (month 3) of the double-blind epoch.

[figure not shown]

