The exposure- adjusted subject incidence rate for a given event in a given period is defined as the number of subjects with at least one reported occurrence of the event in a given time period divided by total subject years at risk in that period. The time at risk for each subject will differ for each adverse event. For subjects with events, only the time until the first event contributes to the total subject years at risk. For subjects who do not experience the event, the time at risk will be calculated based on the safety analysis study window. This rate will be presented per 100 subject years. For subjects with multiple occurrences of the same event, the event will be only counted once per subject.

Time at risk

The time at risk matches the time generally considered for safety summaries except SAEs. In particular, it will be used in the analysis of adverse events to derive (exposure-adjusted) incidence rates.

Prior and concomitant medication

Prior medication will be defined as any non-study medication taken prior to the first dose of the randomized study medication, irrespective of whether the medication continued into the treatment period.

Any non-study medication administered at least once between the day of first dose of randomized study medication and end of the study will be a concomitant medication.

Analysis windows

In general, by-visit analyses, including evaluable scheduled and unscheduled data, will be conducted using analysis windows. Analysis windows will align with the scheduled visit day for each assessment and have its lower and upper bounds symmetrically between the analysis window midpoints (i.e. the scheduled visit day for the particular assessment).

For efficacy parameters: In case of multiple assessments within a analysis window, the scheduled visit will be used regardless of the distance from the target day. Unscheduled visit will only be used when there is no measurement from the scheduled visit in the defined window. In that case the assessment value closest to the scheduled visit day will be used. In case of equal distances, the latest assessment value will be used. The exception is an assessment at early study withdrawal visits along with another assessment within a window. In such cases the early-withdrawal assessment will be used.

For safety parameters: in case of competing assessments within a analysis window, the last one closest to the scheduled visit day will be used.

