“Unable to do” and frequency items ranging from “None of the time” to “All of the time.” These are assigned scores from 1 to 5, with 5 representing the greatest burden. For each domain, the scores will be calculated as the sum of the item responses and the sum will be rescaled to a 0 - 100 scale, with higher scores representing greater impact of migraine (ie, higher burden). There will be a score for each of the two domains and a third score for the stand-alone item. The recall period is the past 24 hours. Please refer to [Section 2.10](#) and [Appendix E.1](#) for details.

Subjects will complete the MPFID every day using the eDiary during DBTE.

Monthly average MPFID score is defined as the sum of observed MPFID scores divided by the total number of observed MPFID scores between each monthly IP dose. Monthly average MPFID score at baseline is the average MPFID score in the baseline period.

Change from baseline in monthly average physical impairment scores as measured by the MPFID in the last month of the double-blind treatment epoch

Calculated based on the following: (monthly average physical impairment scores as measured by the MPFID in the last month of the DBTE) – (baseline monthly average physical impairment scores as measured by the MPFID)

Change from baseline in monthly average impact on everyday activities scores as measured by the MPFID in the last month of the double-blind treatment epoch

Calculated based on the following: (monthly average impact on everyday activities scores as measured by the MPFID in the last month of the DBTE) – (baseline monthly average impact on everyday activities scores as measured by the MPFID)

[REDACTED]

[REDACTED]

[REDACTED]

[REDACTED]

[figure not shown]
[REDACTED]

[figure not shown]
[REDACTED]

[Redacted]

[Redacted]

[Redacted]

Safety Endpoints

Treatment-Emergent Adverse Event (TEAE)

Adverse Events (AEs) recorded on the Adverse Events eCRF page that occurs on or after first dose of investigational product as determined by the flag indicating if the adverse event started prior to the first dose on the Adverse Events eCRF and up to and including 112 days after the end of IP (16 weeks after the last dose of IP).

Serious Adverse Event (SAE)

SAEs determined by the flag indicating if the adverse event is serious on the Adverse Events eCRF page will include those that occur after signing of the informed consent and up to and including end of study.

Serious Treatment-Emergent Adverse Event

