5.9 Appendix D: Visit schedules and assessments

Table 14 Assessment Schedule: Double-Blind Treatment

Epoch	Screen	Baseline ³	Double-Blind Treatment ^{1,4}				Follow-Up ²	Notes
			101	102	103	199		
Visit	1	2	101	102	103	199	301	Follow up visit is 16 weeks after last dose of IMP (V103 / Wk 8), which is 12 weeks after last DBT visit (V199 / Wk 12).
Week	-6	-4	Day 1	4	8	12/PSD/TD	24/FU	
Obtain Informed Consent	X							
Randomization			X					
Demography	X							
Medical & Medication History	X							Including prior prophylactic migraine medication
Treatment Failure Confirmation	X							
Complete Physical Exam	S					S	S	
Brief Physical Exam		S	S	S	S			
Height	X							
Weight	X		X			X	X	
Vital Signs ⁵	X	X	X	X	X	X	X	
Chemistry/Hematology	X		X			X	X	
Serum Pregnancy	X					X		
Urine Pregnancy		X	X	X	X		X	
ECG	X		X	X		X		
Anti-AMG Antibodies			X			X	X	
eDiary Dispensing		S						
eDiary Return			S	S	S	S		Pt brings to each visit for use at site
Clinical Outcomes (eDiary)		Daily (Migraine days, duration, severity, rescue medication)						
MPFID (eDiary)		Daily						
C-SSRS	X	X	X	X	X	X	X	Should also be performed at unscheduled visits.
Concomitant Medications	X	X	X	X	X	X	X	
Adverse Events ⁷			X	X	X	X	X	
Serious Adverse Events ⁷	X	X	X	X	X	X	X	
Study Drug Administration ⁸			X	X	X			
Contact IRT ⁹	X	X	X	X	X	X		
Screening Phase	X							

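### Minor: for patients with no open-label dose, SAP Table 4 closes the double-blind safety phase 84 days after the last dose, although the SAP's own treatment-emergent window, AE collection and the follow-up visit run to 112 days.

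*SAP*

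**What the plan says.** **Phase window.** SAP section 2.1.1 introduces Table 4 with "For safety analyses which are summarized by study phase, analysis windows will be set up based on study phase". Patients who enter open label leave the double-blind phase on the day before their first open-label dose. All others leave it at "MIN(EoS Date, last IP dose date + 84 days) for subjects did not receive any OLTE IP dose", where EoS is the patient's end-of-study date.

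**Time at risk.** In the same section, for patients without the event, "the time at risk will be calculated based on the safety analysis study window". SAP 2.7.1 tabulates TEAE incidence and exposure-adjusted incidence for the double-blind epoch.

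**TEAE window.** SAP 2.1.2 counts an event as treatment-emergent from the first dose "up to and including 112 days after the end of IP (16 weeks after the last dose of IP".

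**AE collection.** Footnote 10 to Protocol Table 6-2 collects non-serious AEs "through the end of the Follow-Up Epoch (16 weeks after the last dose of study drug". Protocol Table 6-1 marks AEs at Visit 301.

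**Follow-up visit.** SAP 1.1 says "a Follow-Up Visit 16 weeks after the last dose of AMG 334 will be required as part of routine safety monitoring", and Protocol 5.6.1 says "a safety follow-up visit (visit 301) should be conducted 16 weeks after the last AMG 334A dose administration". SAP Appendix D, Table 14, adds "Follow up visit is 16 weeks after last dose of IMP (V103 / Wk 8), which is 12 weeks after last DBT visit".

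**Later reporting.** SAP 2.1 plans a second set of analyses that includes Follow-Up Epoch data. SAP section 1 leaves the open-label plan to a separate SAP, which is not among the documents.

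**The concern.** Three statements of the post-dose safety period agree on 16 weeks. The window that decides what enters the double-blind tables is four weeks shorter, and no reason is given.

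For patients who go on to open label, an early cut makes sense, because their later events pass to the open-label phase. Patients with no open-label dose have no such place. They are not in the open-label analysis set, which requires an open-label dose (Protocol 9.1). Protocol 9.5.2 names only the double-blind epoch and the combined open-label epochs for safety analysis, and Table 4 has no follow-up phase.

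An event can therefore be treatment-emergent by definition, be collected at a required visit, and still appear in no safety table that this SAP specifies. Those affected stopped early or chose not to continue, and a safety reader would want their late events accounted for.

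**Working it through.** **1. The two windows**
- 16 weeks × 7 = 112 days, which reproduces the SAP's own pairing of the two figures.
- 84 / 7 = 12 weeks.
- Gap: 112 − 84 = 28 days, or 28 / 112 = 25% of the post-dose TEAE period for an affected patient.

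**2. On the study calendar** (doses on target days)

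| Last dose | Table 4 closes (+84) | TEAE window and follow-up visit (+112) |
|---|---|---|
| Day 1 | Day 85 | Day 113 |
| Day 29 (Week 4) | Day 113 | Day 141 |
| Day 57 (Week 8) | Day 141 | Day 169 |

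Day 169 is Week 24 (24 × 7 + 1), which matches Visit 301. A patient who attends that visit has EoS at about +112 days, so the minimum always selects +84. The minimum helps only where the patient left before day 84, and then nothing is lost.

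**3. Patients affected**

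The Amendment 3 rationale in the protocol gives 246 randomised, 242 completing the double-blind epoch and 240 continuing.
- Non-completers: 246 − 242 = 4.
- Completers who did not continue: 242 − 240 = 2.
- Total: at most 6, and 6 / 246 = 2.4%.

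This assumes that continuing means receiving an open-label dose.

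**4. Person-time over full follow-up**
- Ceiling: 6 × 28 = 168 person-days; 168 / 365.25 = 0.46 patient-years.
- Only the two completers followed to day 112: 2 × 28 = 56.
- Nobody followed past day 84: 0.

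Total double-blind time on Table 4's windows, assuming all were dosed on target days:
- All six last dosed on Day 57: 240 × 84 + 6 × 141 = 21,006. Then 168 / 21,006 = 0.80% and 56 / 21,006 = 0.27%.
- All six dosed on Day 1 only: 240 × 84 + 6 × 85 = 20,670. Then 168 / 20,670 = 0.81%.

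**5. What the double-blind lock allows**

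SAP 1.1 locks the database when the last patient completes the double-blind epoch. The amendment rationale gives first screening on 20 March 2017 and enrolment complete on 6 July 2017. Assume that 6 July is the last randomisation, that data are cut on that patient's Day 85, and that the first patient had no screening interval before the 4-week baseline.
- Cut: 6 July + 84 days = 28 September 2017.
- Earliest randomisation: 20 March + 28 days = 17 April. Day 141 is 4 September and Day 169 is 2 October.
- Most that a patient last dosed on Day 57 can regain: 4 to 28 September = 24 days.
- Randomised on 11 May: Day 141 = 11 May + 140 days = 28 September, so nothing is regained from then on.

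An earlier last dose or a later cut recovers more, up to 28 days each. For example, if 6 July were instead the last entry to baseline, the cut would fall 28 days later, on 26 October. A Day-57 patient randomised by 11 May would then regain all 28 days.

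**The case against.** **The windows do different jobs.** One flags an event as treatment-emergent and the other allots data to a phase, so a narrower phase window is not in itself a contradiction. For the 240 continuers, Table 4 stops about 28 days after the Week 8 dose, so their double-blind tables never cover 112 post-dose days either. This stands for continuers, whose later events move to the open-label phase. It does not explain the cut for patients with no later phase.

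**Later reporting may cover it.** The planned analysis with Follow-Up Epoch data, or the separate open-label SAP, may report these events. This stands in part: nothing shows that no plan exists. But it does not make the double-blind tables match the SAP's own TEAE period.

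**Another repair is possible.** The SAP could keep 84 days and state where days 85 to 112 are reported. That would end the silence but leave the tables short of the definition. Also, the TEAE sentence counts from the end of IP before its parenthesis names the last dose, while SAP 2.1.3 defines end of IP as a decision date. The comparison here uses the last dose, as the parenthesis and Table 4 do.

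**Stronger readings that the documents do not support**
- *Events are lost.* They are collected to 16 weeks and are due to enter a later analysis.
- *Rates are distorted by a 112-day numerator over an 84-day denominator.* Events and time at risk share the Table 4 window, so the rate is coherent. It only covers a shorter period than the definition.
- *SAEs are affected in the same way, or their window is contradictory.* SAEs are defined to end of study and excepted from the time-at-risk rule, yet are tabulated for the double-blind epoch. That is a matter of missing detail and adds nothing to this point.
- *The full 168 person-days would return to the double-blind tables.* The lock limits what can return.

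**Conclusion.** The inconsistency is real and minor. For non-continuers a stated rule excludes from the double-blind TEAE tables, and from the time at risk, up to 28 days that the same SAP calls treatment-emergent.

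Its size is very small and possibly zero: no more than 6 patients and 168 person-days over full follow-up, and less in the double-blind analysis under a cut at about 28 September 2017. These figures rest on three assumptions: that continuing meant being dosed, that doses fell on target days, and that the cut falls at the last patient's Day 85. Safety is descriptive (SAP 2.7 rules out between-arm testing), so no safety test changes and no efficacy result is touched.

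The source of the 84 days is not stated. The follow-up visit is 12 weeks after the Week 12 visit, and those 12 weeks may have been applied to the last dose instead. That is only an inference, and the point does not depend on it.

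**What to change.** In SAP Table 4, for patients with no open-label dose, change the limit from 84 to 112 days after the last dose. Keep the minimum with EoS, and cut at the double-blind lock if the window is still open. Use this one window for both events and time at risk.

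Add a sentence that follow-up events arriving after the lock are reported in the planned later analysis, by the safety set's treatment assignment, without reopening the locked double-blind tables.

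The cost is one number and a sentence or two, with no new data collection. The downside is slightly more off-drug time at risk for a few non-continuers.
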